5.2. Exclusion Criteria

MEDICAL CONDITIONS

- 1. Clinically significant abnormalities, aside from chronic HBV infection in medical history (e.g., moderate-severe liver disease other than chronic HBV, acute coronary syndrome within 6 months of screening, major surgery within 3 months of screening, significant/unstable cardiac disease, uncontrolled diabetes, bleeding diathesis or coagulopathy) or physical examination
- 2. Co-infection with:
 - a. Current or past history of Hepatitis C virus (HCV)
 - b. Human immunodeficiency virus (HIV)
 - c. Hepatitis D virus (HDV)
- 3. History of or suspected liver cirrhosis and/or evidence of cirrhosis as determined by
 - a. both Aspartate aminotransferase (AST)-Platelet Index (APRI) >2 and FibroSure/FibroTest result >0.7
 - i. If only one parameter (APRI or FibroSure/FibroTest) result is positive, a discussion with the Medical Monitor is required before inclusion in study is permitted
 - b. Regardless of APRI of Fibrosure/FibroTest score, if the participant meets one of the following historical criteria, they will be excluded from the study
 - i. Liver biopsy (i.e., Metavir Score F4)
 - ii. Liver stiffness >12 kPa
- 4. Diagnosed or suspected hepatocellular carcinoma as evidenced by the following
 - a. Alpha-fetoprotein concentration ≥200 ng/mL
 - b. If the screening alpha fetoprotein concentration is ≥50 ng/mL and <200 ng/mL, the absence of liver mass must be documented by imaging within 6 months before randomization
- 5. History of malignancy within the past 5 years with the exception of specific cancers that are cured by surgical resection (e.g., skin cancer). Participants under evaluation for possible malignancy are not eligible.
- 6. History of vasculitis or presence of symptoms and signs of potential vasculitis [e.g., vasculitic rash, skin ulceration, repeated blood detected in urine without identified cause] or history/presence of other diseases that may be associated with vasculitis condition (e.g., systemic lupus erythematosus, rheumatoid arthritis, relapsing polychondritis, mononeuritis multiplex)
- 7. History of extrahepatic disorders possibly related to HBV immune conditions (e.g., nephrotic syndrome, any type of glomerulonephritis, polyarteritis nodosa, cryoglobulinaemia, uncontrolled hypertension)
- 8. Positive (or borderline positive) ANCA at screening:
 - a. Participants that meet this criteria may be considered for inclusion in the study following:
 - i. Analysis of MPO-ANCA [pANCA] and PR3-ANCA [cANCA] AND
 - ii. A discussion with the Medical Monitor to review participant's complete medical history to ensure no past history or current manifestations of a

vasculitic/inflammatory/auto-immune condition

- 9. Low C3 at screening AND evidence of past history or current manifestations of vasculitic/inflammatory/auto-immune conditions
 - a. All participants with low C3 at screening should have their medical history discussed with the Medical Monitor prior to enrolment
- 10. History of alcohol or drug abuse/dependence
 - a. Current alcohol use as judged by investigator to potentially interfere with participant compliance
 - b. History of or current drug abuse/dependence as judged by the investigator to potentially interfere with participant compliance
 - Refers to illicit drugs and substances with abuse potential. Medications that are used by the participant as directed, whether over-the-counter or through prescription, are acceptable and would not meet the exclusion criteria

PRIOR/CONCOMITANT THERAPY

- 11. Currently taking, or took within 3 months of screening, any immunosuppressing drugs (e.g., prednisone), other than a short course of therapy (≤2 weeks) or topical/inhaled steroid use.
- 12. Participants for whom immunosuppressive treatment is not advised, including therapeutic doses of steroids, will be excluded
- 13. Currently taking, or took within 12 months of screening, any interferon-containing therapy.
- 14. Participants requiring anti-coagulation therapies (for example warfarin, Factor Xa inhibitors or anti-platelet agents like clopidogrel)

PRIOR/CONCOMITANT THERAPY

- 15. The participant has participated in a clinical trial and has received an investigational product within the following time period prior to the first dosing day in the current study: 5 half-lives (if known) or twice the duration (if known) of the biological effect of the study treatment (whichever is longer) or 90 days (if half-life or duration is unknown).
- 16. Prior treatment with any oligonucleotide or small interfering RNA (siRNA) within 12 months prior to the first dosing day

DIAGNOSTIC ASSESSMENTS

- 17. Fridericia's QT correction formula (QTcF) ≥450 msec (if single electrocardiogram [ECG] at screening shows QTcF ≥450 msec, a mean of triplicate measurements should be used to confirm that participant meets exclusion criterion).
- 18. Laboratory results as follows
 - a. Serum albumin <3.5 g/dL

- b. Glomerular filtration rate (GFR) <60 mL/min /1.73m² as calculated by the CKD-EPI formula (for Japan, JSN-CKDI equation).
- c. INR >1.25
- d. Platelet count <140 X 10⁹/L
- e. Total bilirubin >1.25 x ULN
 - i. For participants with benign unconjugated hyperbilirubinemia with total bilirubin >1.25 x ULN, discussion for inclusion to the study is required with the Medical Monitor
- f. Urine albumin to creatinine ratio (ACR) ≥0.03 mg/mg (or ≥30 mg/g). In the event of an ACR above this threshold, eligibility may be confirmed by a second measurement
 - i. In cases where participants have low urine albumin and low urine creatinine levels resulting in a urine ACR calculation ≥0.03 mg/mg (or ≥30 mg/g), the investigator should confirm that the participant does not have a history of diabetes, hypertension or other risk factors that may affect renal function and discuss with the Medical Monitor, or designee

OTHER EXCLUSIONS

19. History of/sensitivity to GSK3228836 or components thereof or a history of drug or other allergy that, in the opinion of the investigator or Medical Monitor, contraindicates their participation

5.3. Lifestyle Considerations

5.3.1. Alcohol and Tobacco

During each dosing session, participants will abstain from alcohol for 24 hours before the start of each scheduled clinic visit until after they leave the clinic.

Participants who use tobacco products will be instructed that use of nicotine-containing products (including nicotine patches and other delivery devices such as vaporizers) will not be permitted while they are in the clinical unit.

5.3.2. Activity

Participants will abstain from strenuous exercise for 48 hours before each blood collection for clinical laboratory tests. For the duration of the study, until final follow-up, participants are encouraged to refrain from changing their activity beyond that which they normally perform. Additionally, participants will abstain from taking creatine-containing exercise supplements for all parts of the study.

5.4. Screen Failures

Screen failures are defined as participants who consent to participate in the clinical study but are not subsequently randomized. A minimal set of screen failure information is required to ensure transparent reporting of screen failure participants to meet the Consolidated Standards of Reporting Trials (CONSORT) publishing requirements and to respond to queries from regulatory authorities. Minimal information includes demography, screen failure details, eligibility criteria, any protocol deviations and any serious adverse events (SAEs).

Individuals who do not meet the criteria for participation in this study (screen failure) may not be rescreened unless discussed and agreed with the Medical Monitor. Individuals who fall out of the screening window, may be rescreened at the discretion of the investigator and site.

5.5. Additional Participant Enrollment

The planned number of participants will be approximately 440.

In the case of a disruptive event (e.g., COVID-19, natural disaster), sites and/or participants may be unable to conduct/attend dosing visits, conduct/attend follow-up visits, participants may be discontinued from study treatment, and/or participants may be withdrawn from the study.

The study may enrol additional participants to within 10% of the planned 440 participants to support a sufficient safety database.

6. STUDY INTERVENTION

Study intervention is defined as any investigational intervention(s), marketed product(s), placebo, or medical device(s) intended to be administered to a study participant according to the study protocol.

6.1. Study Intervention(s) Administered

Study Treatment

Study Treatment							
Product Name:	GSK3228836 Placebo						
Formulation Description:	Clear colorless to slightly yellow solution Clear colorless solution						
Dosage Form:	Solution for injection Solution for in						
Unit Dose Strength(s)/Dosage Level(s):	150mg/mL; 1.0mL nominal volume per vial (minimal overfill per vial)	Placebo					
Route/Administration/Duration:	SC, multiple (once weekly, up to 168 days, plus loading doses)	SC, multiple (once weekly, up to 168 days, plus loading doses)					
Dosing Instructions:	Administer two SC injections of GSK3228836 for 300 mg dose, one SC injection of GSK3228836 for 150 mg dose (plus one SC placebo dose for blinding purposes)	Administer two SC injections for placebo					
Manufacturer/Source of Procurement:	GSK GlaxoSmithKline Manufacturing SpA, Parma (Italy)	Locally sourced normal Saline					
Method for Individualizing Dosage	Dispensing into syringes	Dispensing into syringes					

SC=subcutaneous

The site of injection will be recorded for each participant and dose(s). Sites of injection are listed in order of preference and are a guide for the clinical staff.

- 1. Abdominal quadrants
- 2. Thighs
- 3. Outer area of the upper arms
- 4. Buttocks

Injections should be rotated within each anatomical site or site(s) of injection should be changed administration-to-administration. Injection into areas with ongoing injection site reactions should be avoided.

6.2. Preparation/Handling/Storage/Accountability

The investigator or designee must confirm appropriate temperature conditions have been maintained during transit for all study intervention received and any discrepancies are reported and resolved before use of the study intervention.

Only participants enrolled in the study may receive study intervention and only authorized site staff may supply or administer study intervention. All study interventions must be stored in a secure, environmentally controlled, and monitored (manual or automated) area in accordance with the labeled storage conditions with access limited to the investigator and authorized site staff.

The investigator, institution, or the head of the medical institution (where applicable) is responsible for study intervention accountability, reconciliation, and record maintenance (i.e., receipt, reconciliation, and final disposition records).

Further guidance and information for the final disposition of unused study intervention are provided in the Study Reference Manual.

Under normal conditions of handling and administration, study intervention is not expected to pose significant safety risks to site staff. Take adequate precautions to avoid direct eye or skin contact and the generation of aerosols or mists. In the case of unintentional occupational exposure notify the monitor, Medical Monitor and/or GSK study contact.

A Material Safety Data Sheet (MSDS)/equivalent document describing occupational hazards and recommended handling precautions either will be provided to the investigator, where this is required by local laws, or is available upon request from GSK.

6.4. Study Intervention Compliance

When participants are dosed at the site, they will receive study intervention directly from the investigator or designee, under medical supervision. The date and time of each dose administered in the clinic will be recorded in the source documents. The dose of study intervention and study participant identification will be confirmed at the time of dosing by a member of the study site staff other than the person administering the study intervention.

6.5. Concomitant Therapy

Any medication or vaccine (including over-the-counter or prescription medicines, vitamins, and/or herbal supplements or other specific categories of interest) that the participant is receiving at the time of enrollment or receives during the study must be recorded along with:

- reason for use
- dates of administration including start and end dates
- dosage information including dose and frequency

The Medical Monitor should be contacted if there are any questions regarding concomitant or prior therapy.

Concomitant medications, including NAs (see Section 6.5.2 and Section 6.5.3), should be recorded.

Traditional Chinese medicine (TCM) and/or acupuncture as it relates to CHB therapy should be avoided during the duration of the study. If participants report use of TCM and/or acupuncture, then details must be recorded in the concomitant medication case report form (CRF).

6.5.1. Nucleos(t)ide Treatment during and after the End of the Study

The investigator is responsible for ensuring that consideration has been given to the care of the participant's medical condition, and that participants are able to continue (for participants on NA therapy at Baseline, participants are expected to continue their NA therapy over the duration of the study) and/or start standard of care treatment during the study period.

The investigator is responsible for ensuring that consideration has been given to the post-study care of the participant's medical condition, whether or not GSK is providing specific post-study treatment.

For participants who are not receiving NA therapy at baseline, initiate NA therapy if ALT ≥3x ULN and bilirubin >1.5x ULN, as per Section 7.1.1 (Liver Chemistry Monitoring and Stopping Criteria). NA therapy may be subsequently discontinued if other tests (e.g., HBV DNA, HBsAg) rule out hepatitis B flare.

6.5.2. Initiation of Nucleos(t)Ides During GSK3228836 Treatment

The barrier to development of GSK3228836 resistance is unknown. Population sequencing of isolates from Study ISIS 505358-CS3 did not detect the development of mutations in the GSK3228836 binding site following 4 weeks of GSK3228836 monotherapy.

The risk of resistance development is expected to be lowest in participants receiving concomitant NA therapy due to the suppression of HBV viral replication. Ongoing viral replication during GSK3228836 treatment (e.g., due to virological breakthrough) may increase the risk of the development of resistance. Investigators should therefore consider initiation of NAs for participants not already receiving concomitant NA therapy and experience virological breakthrough whilst still receiving GSK3228836 (i.e., haven't completed treatment).

Virological breakthrough is defined as one of the following confirmed (2 sequential visits) lab results:

- ≥1 log increase from nadir of HBV DNA
- HBV DNA becoming quantifiable after being below the LLOQ

Initiation of NA therapy should also be considered for participants who are not receiving NA therapy at baseline, but are having either no response or only a partial response to GSK3228836 treatment (i.e. Treatment Arms 1 to 3, but not Arm 4 in participants not

currently on NA therapy). In Arm 4 of the participants not currently on NA therapy, NA will be withheld only during the initial 12-week placebo period. During the latter part of the study when the participants in Arm 4 are receiving active GSK3228836, NA therapy may be initiated as above if there is concern about developing resistance to GSK3228836.

No response to GSK3228836 treatment is defined as:

• By Week 12, <1 log decline in HBV DNA level from baseline

Partial response to GSK3228836 treatment is defined as:

• >1 log decline in HBV DNA, but subsequent plateau of HBV DNA levels such that achievement of HBV DNA below the LLOQ is considered unlikely

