Text has also been included to allow additional interim analyses prior to the end of study (after all participants have completed treatment) to support asset development planning and decision making.

In addition, minor typographical errors and inconsistencies have been corrected and minor editorial changes have been made. Changes made to the text body have been made concurrently in the synopsis.

Section # and Name	Description of Change	Brief Rationale
Section 6.5.1 NA Treatment during and after the End of the Study; Section 7.1.1 Liver Chemistry Monitoring and Stopping Criteria Table 6	Added text: For participants who are not receiving NA therapy at baseline, initiate NA therapy if ALT ≥3x ULN and bilirubin >1.5x ULN, as per Section 7.1.1 (Liver Chemistry Monitoring and Stopping Criteria). NA therapy may be subsequently discontinued if other tests (e.g., HBV DNA, HBsAg) rule out hepatitis B flare.	As per regulatory request in consideration of participant safety.
Section 9.5 Interim Analyses	Added text: Additional interim analyses may be conducted after the third interim (at which time all participants will have completed treatment and sponsor staff [as specified in the blinding plan] will be unblinded), to support development planning and decision making. If conducted, these analyses will be unblinded to the sponsor staff (as specified in the blinding plan) and referenced in the clinical study report.	To allow further review of the data prior to end of study (after all participants have completed treatment).

TABLE OF CONTENTS

				PAGE
1.	PROT	TOCOL S	UMMARY	8
	1.1.	Synops	is	8
	1.2.		a	
	1.3.		lle of Activities (SoA)	
2.	INTR	ODUCTIO	ON	21
	2.1.		Rationale	
	2.2.		ound	
	2.3.		/Risk Assessment	
		2.3.1.	Risk Assessment	23

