4. STUDY DESIGN

4.1. Overall Design

This is a Phase 2b, multi-center, randomized, partial-blind [Sponsor and Participant blinded], study to assess efficacy and safety of treatment with GSK3228836 in two populations of patients with CHB (1) participants on stable nucleos(t)ide treatment and (2) participants not currently on nucleos(t)ide therapy.

Both populations of patients with CHB will be randomized into one of 4 parallel arms:

- 300 mg GSK3228836 once/week for 24 weeks (plus loading dose of 300 mg GSK3228836 on Day 4 and Day 11);
- 300 mg GSK3228836 once/week for 12 weeks (plus loading dose of 300 mg GSK3228836 on Day 4 and Day 11) followed by step-down in dose of 150 mg (plus placebo to match to maintain participant blinding) GSK3228836 once/week for 12 weeks;
- 300 mg GSK3228836 once/week for 12 weeks (plus loading dose of 300 mg GSK3228836 on Day 4 and Day 11) followed by placebo once/week for 12 weeks;
- Placebo once/week for 12 weeks followed by 300 mg GSK3228836 once/week for 12 weeks (plus placebo loading doses to match on Day 4 and Day 11, no loading dose for GSK3228836 treatment)

After the 24 weeks of dosing with GSK3228836 or placebo, there will be a post-treatment follow-up period of 24 weeks.

Populations will be stratified based on HBsAg level (HBsAg \leq 3 log IU/mL and \geq 3 log IU/mL) and whether participants are HBeAg positive or negative.

The study is a partially blinded study where participants will be blinded to the study treatment. The investigators, site staffs and pharmacist will be unblinded. GSK and contract research organization (CRO) team members will be blinded to participants' study treatment and any potentially unblinding information, unless specified otherwise in the study blinding management plan (e.g., unblinded site monitors).

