5.1. Inclusion Criteria

AGE

1. At least 18 years of age at the time of signing the informed consent [if country/site age requirements for consent differ, the more stringent (e.g., higher age) restriction will be required for that country/site].

TYPE OF PARTICIPANT AND DISEASE CHARACTERISTICS

- 2. Participants who have documented chronic HBV infection ≥6 months prior to screening AND
 - a. Not currently on nucleos(t)ide analogue therapy population defined as participants who never received HBV treatment (treatment naïve) OR must have ended nucleos(t)ide therapy at least 6 months prior to the

screening visit

- b. OR Currently receiving stable nucleos(t)ide analogue therapy population defined as no changes to their nucleos(t)ide regimen from at least 6 months prior to screening and with no planned changes to the stable regimen over the duration of the study
- 3. Plasma or serum HBsAg concentration >100 IU/mL
- 4. Plasma or serum HBV DNA concentration
 - a. Participants not currently on nucleos(t)ide analogue therapy, plasma or serum HBV DNA >2000 IU/mL
 - Participants who are receiving stable nucleos(t)ide analogue therapy must be adequately suppressed, defined as plasma or serum HBV DNA <90 IU/mL
- 5. Alanine Transaminase (ALT)
 - a. ALT for treatment naïve participants and for participants who are not currently receiving treatment
 - i. ALT <3 X ULN will be included initially
 - If agreed by the IDMC after review of safety data, the ALT inclusion criteria may be expanded to include participants with ALT <5 X ULN
 - b. ALT ≤2 X ULN for participants who are receiving stable nucleos(t)ide analogue therapy

SEX

- 6. Male and/or Female
 - a. A male participant is eligible to participate if they agree to the following during the intervention period and for at least 90 days after the last dose of study treatment
 - i. Refrain from donating sperm
 - ii. AND be abstinent from heterosexual intercourse as their preferred and usual lifestyle (abstinent on a long term and persistent basis) and agree to remain abstinent OR Must agree to use contraception/barrier as detailed below
 - 1. Agree to use a male condom [and should also be advised of the benefit for a female partner to use a highly effective method of contraception as a condom may break or leak] when having sexual intercourse with a woman of childbearing potential who is not currently pregnant
 - b. A female participant is eligible to participate:

- i. If she is not pregnant or breastfeeding

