7.1.1. Liver Chemistry Monitoring and Stopping Criteria

Liver chemistry monitoring and stopping criteria have been designed to assure participant safety and to evaluate liver event etiology. Study intervention will be discontinued for a participant if the liver stopping criteria are met. Restart/re-challenge guidelines are presented in Section 10.6.

Discontinuation of study intervention for abnormal liver tests is required when:

- a participant meets one of the discontinuation conditions outlined in Table 6
- when in the presence of abnormal liver chemistries not meeting protocol-specified stopping rules, the investigator believes study intervention discontinuation is in the best interest of the participant.

Table 6 lists the criteria for withholding or discontinuing the study medication in a study participant with elevation of ALT. Additional testing will be performed (see safety follow-up procedures for participants who meet increased monitoring or stopping criteria) and the participant monitored until liver chemistry abnormalities resolve, stabilize, or return to within baseline values. The participant must then attend the follow-up visits specified in the SoA.

Every attempt must be made to have the participant evaluated (within 24 hours) for repeat assessment of liver chemistries and additional testing and close monitoring (a specialist or hepatology consultation is recommended). Participants must be monitored twice weekly until liver chemistry abnormalities (ALT, AST, alkaline phosphatase, bilirubin)

resolve, stabilize, or return to within baseline values. Upon completion of the safety follow-up procedures (see below), the participant must attend the follow-up visits specified in the SoA.

Table 6 Liver Chemistry Monitoring and Stopping Criteria-

ALT Level	Monitoring Plan	Discontinuation
10x ULN ≤ ALT <12x ULN and Bilirubin ≤1.5x ULN and INR ≤1.5 (if available)	Monitor twice weekly Additional lab assessments	Permanently discontinue IMP if ALT >10x ULN >4 weeks

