ALT ≥12x ULN and Bilirubin≤1.5x ULN and INR ≤1.5 (if available) ALT ≥3x ULN and	Hold dose Monitor twice weekly Additional lab assessments if not already done Take off hold: 150 mg SC weekly when ALT <10x ULN; increasing dose to 300 mg (if applicable) should be agreed with Medical Monitor Hold dose Monitor twice weekly Additional lab assessments if not	Permanently discontinue IMP if any of the following apply: ■ ALT ≥10x ULN >4 weeks ■ ALT ≥12x ULN recurs after IMP taken off hold Permanently discontinue IMP if the following recurs
1.5x ULN <bilirubin (="" uln="" ≤2x="">35% direct) and INR ≤1.5 (if available)</bilirubin>	already done Take off hold: 150 mg SC weekly when bilirubin returns to <1.5x ULN; increasing dose to 300 mg (if applicable) should be agreed with Medical Monitor For participants not receiving NA therapy at baseline, initiate NA therapy¹	after IMP taken off hold: 1.5x ULN <bilirubin (="" uln="" ≤2x="">35% direct) And INR ≤1.5 (if available)</bilirubin>
ALT ≥3x ULN and any of the following apply: • bilirubin >2x ULN (>35% direct) • associated with the appearance or worsening of hepatitis symptoms • INR >1.5 (if available)		Permanently discontinue IMP Monitor twice weekly until stable ALT Additional lab assessments if not already done For participants not receiving NA therapy at

ALT Level	Monitoring Plan	Discontinuation
		baseline, initiate NA therapy¹

ALT = alanine aminotransferase; IMP = investigational medicinal product; ULN = upper limit of normal 1. NA therapy may be subsequently discontinued if other tests (e.g., HBV DNA, HBsAg) rule out hepatitis B flare.

*Notes:

- Any abnormal laboratory parameters that meet the criteria for individual treatment discontinuation must be confirmed by retest of a new collection of blood samples as soon as possible.
- Deterioration considered clinically significant from the baseline in the liver parameters must be confirmed by retesting ALT, total bilirubin, direct bilirubin, and INR (if available).
- If one criterion in the list above is met and confirmed by retesting, further treatment may be discontinued for this participant after discussion with the Medical Monitor. Results of retesting must be evaluated before the next dose is administered.
- Monitor participant until liver chemistry abnormalities resolve, stabilize, or return to within baseline values.

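### Protocol 6.5.2 withholds nucleos(t)ide therapy in Arm 4 during the placebo period without an exception for the liver-safety starts required by 6.5.1 and Table 6

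*Protocol*

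**What the plan says.** Three places in the protocol govern NA starts in participants who enter off NA.

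- **Section 6.5.2** advises investigators to consider NA for virological breakthrough, no response or partial response. It excludes Arm 4 from the response-based advice and adds that "NA will be withheld only during the initial 12-week placebo period". Once Arm 4 is on active drug, NA may be started if resistance is a concern.
- **Section 6.5.1** is an instruction for participants not on NA at baseline: "initiate NA therapy if ALT ≥3x ULN and bilirubin >1.5x ULN".
- **Table 6 in Section 7.1.1** repeats the instruction in two rows: "For participants not receiving NA therapy at baseline, initiate NA therapy". One row holds dosing (ALT ≥3x ULN, bilirubin above 1.5x and up to 2x ULN). The other discontinues treatment permanently (ALT ≥3x ULN with bilirubin >2x ULN, hepatitis symptoms or INR >1.5).

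The amendment summary gives the reason for the liver-safety text: "As per regulatory request in consideration of participant safety".

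**The concern.** Neither 6.5.1 nor Table 6 exempts Arm 4 or the placebo period. Section 6.5.2 has no safety exception and no cross-reference to either. A site with an Arm 4 participant in Weeks 1 to 12 who meets the liver criteria can find one section saying NA is withheld and another saying it must be started.

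At stake is timely antiviral treatment during a possible hepatitis B flare. These participants enter untreated with HBV DNA above 2000 IU/mL (Section 5.1). The restriction can be acted on at the site, because "The investigators, site staffs and pharmacist will be unblinded".

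**Working it through.** The point is textual, so the check is whether both rules can apply to the same participant at the same time.

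1. **Who.** The 6.5.2 sentence covers Arm 4 of the not-on-NA population. Section 6.5.1 and Table 6 cover every participant not on NA at baseline. The first group lies inside the second.
2. **When.** The 6.5.2 sentence covers the first 12 weeks. Section 6.5.1 and Table 6 have no time limit. The Section 6 definition of study intervention includes placebo, and Section 7.1.1 is written for study intervention: "Study intervention will be discontinued for a participant if the liver stopping criteria are met". Table 6 itself speaks of IMP and gives its off-hold dose in milligrams, which fits active drug better. Section 6.5.1, however, does not depend on what is being injected.
3. **Whether it would be detected.** Chemistry is scheduled on Days 1, 8, 15, 22, 29, 36, 43 and 50 (Table 2) and Days 57, 64, 71 and 78 (Table 3), so 8 + 4 = 12 samples. Day 1 is the pre-dose baseline, which leaves 11 after placebo starts.
4. **For what reason.** The word *only* in the 6.5.2 sentence limits the duration, not the reason. The surrounding paragraph is about response and resistance, but the sentence does not say that it stops there.
5. **Which prevails.** Neither document says.

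The clash is cleanest in the hold-dose row, where the participant is still within the placebo period. In the permanent-discontinuation row it can be argued that the placebo period ends with the last dose. Section 6.5.2 does not say how the 12 weeks are counted in that case.

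**Size of the group.**

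- Planned: 440 / 2 populations = 220; with 3:3:3:1 allocation, 220 × 1/10 = 22. This reproduces the figure in Protocol 9.2.
- With the extra enrolment allowed in Protocol 5.5: 440 × 1.10 = 484; 484 / 2 × 1/10 = 24.2, or about 24, assuming the same split and ratio.

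Neither document gives a rate of meeting the liver criteria on placebo or of misapplying the rule, so no event count follows.

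**The case against.** The best defence is context. Section 6.5.2 concerns NA during GSK3228836 treatment and opens with resistance. Non-response to a drug not yet given cannot be judged, which explains why Arm 4 is carved out. NA is not on the prohibited list in 6.5.4. Section 6.5.1 also makes the investigator responsible for participants being able to start standard of care. The liver rule is mandatory, specific and newer, and it is printed in the table a site would use for a liver event. The Medical Monitor must be told of such an event within 24 hours. Most sites would follow the safety rule.

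Nearly all of this stands, and it is why the point is minor. It does not remove the gap:

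- The amendment history describes the interval as one of NA restriction, without limiting the reason.
- Where the protocol wants a safety exception it writes one: the immunosuppressant restriction in 6.5.4 carries an explicit exception pointing to Section 7.
- SAP 4.8 records that some participants in this population started NA on Day 1 through misunderstanding the protocol. That error ran the other way and is not evidence that this rule was misapplied. It does weaken reliance on sites inferring intent.

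Two stronger readings are tempting. A reader might infer that the protocol forbids required safety treatment in Arm 4. The documents do not support that, since the elective-only reading is the more natural one. A reader might also take the whole Arm 4 placebo exposure, 22 × 12 = 264 participant-weeks, as the size of the problem. That counts all time on placebo, whereas a conflict needs ALT ≥3x ULN plus raised bilirubin, hepatitis symptoms or raised INR. Entry criteria make this uncommon at the outset: ALT <3x ULN initially (possibly <5x later), INR no higher than 1.25, bilirubin generally no higher than 1.25x ULN, and no cirrhosis.

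**Conclusion.** The inconsistency is real but small. Read literally, 6.5.2 conflicts with the liver-safety NA starts in 6.5.1 and Table 6 during Weeks 1 to 12 of Arm 4 in the not-on-NA population. The likely intent is that only elective starts are withheld, but the text does not say so. The group is about 22 participants (about 24 with extra enrolment), and the probability of a harmful misreading is low and cannot be estimated from the documents.

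The primary analysis is unaffected: its estimands cover Arms 1 to 3, the model is fitted arm by arm, and the Arm 4 SVR assessment is exploratory. A liver-safety NA start in Arm 4 would count as rescue medication under the existing definition (Protocol 9.1, SAP 2) and so as non-response (SAP 4.2.2.2). A reader might infer that SAP 4.2.4.3 already classes it as rescue for medical reasons. That is reasonable, but the SAP does not define the term.

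One limit concerns timing. The SAP version history for February 2022 mentions requests made at the third interim analysis, which required all participants to have completed Week 24. If the Arm 4 placebo periods were over when Protocol Amendment 02 took effect, the gain is a coherent protocol and a sound template for later studies.

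**What to change.** In Protocol 6.5.2, at the end of the sentence that withholds NA during the Arm 4 placebo period, add: *except where NA initiation is required by Section 6.5.1 or Table 6 (Section 7.1.1)*.

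The cost is one clause. It needs no new data, alters no sample size or operating characteristic, and requires no SAP change. If the sponsor wants the classification in SAP 4.2.4.3 to be beyond argument, a few words there could state that liver-safety NA starts are rescue for medical reasons. That is optional.
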